8.0 Study Population

8.1 Inclusion Criteria

- a) Male or female smokers who are 21-65 years of age and are willing to stop smoking and completely switch to e-cigarettes;
- b) Report smoking ≥ 5 cigarettes daily;
- c) Biochemically confirmed regular smoking status by a CO level ≥ 6 ppm, (if < 6 , then NicCheck test of 6 or greater);
- d) Smoking daily for at least 1 year;

- e) No unstable and significant medical or physical conditions as determined by the licensed medical professional (to ensure safety of the subject, to minimize the effects of poor health on biomarker measures and to maximize compliance to study procedures);
- f) No unstable pulmonary illness (COPD, asthma, COVID, current bronchitis) or exacerbation of symptoms in the past 3 months as determined by the licensed medical professional;
- g) Subjects are in stable, good mental health (i.e. not currently, within the past 3 months, experiencing unstable or untreated psychiatric diagnosis, including substance abuse) as determined by the licensed medical professional;
- h) Subjects who are not taking medications that affect relevant metabolic enzymes (as noted on the excluded medication list);
- i) Women who are not pregnant or nursing or planning to become pregnant;
- j) Subject has provided written informed consent to participate in the study.

8.2 Exclusion Criteria

- a) Regular tobacco or nicotine product use (including nicotine replacement) (> 9 days in last 30 days) other than cigarettes;
- b) Currently (within the last week) using nicotine replacement or other products for cessation purposes;
- c) Significant immune system disorders, respiratory diseases, kidney or liver diseases or any other medical disorders that may affect biomarker data;
- d) Excessive drinking (5 or more drinks daily) or problems with drinking or drugs (self-report of binge drinking alcohol or treatment for drug or alcohol abuse within last 3 months); to be assessed by PI or licensed medical professional;
- e) Failure to agree to take adequate protection to avoid becoming pregnant during the study;
- f) Vital signs outside of the following range (participants failing for vital signs will be allowed to re-screen once):
 - Systolic BP greater than or equal to 160 mm/hg
 - Diastolic BP greater than or equal to 100 mm/hg
 - Systolic BP below 90 mm/hg and symptomatic (dizziness, extreme fatigue, difficulty thinking, inability to stand or walk, feeling faint)
 - Diastolic BP below 50 mm/hg and symptomatic (dizziness, extreme fatigue, difficulty thinking, inability to stand or walk, feeling faint)
 - Heart rate greater than or equal to 105 bpm
 - Heart rate lower than 45 bpm and symptomatic (dizziness, extreme fatigue, difficulty thinking, inability to stand or walk, feeling faint)
- g) Expired air carbon monoxide (CO) level greater than 80 ppm;
- h) Self-reported allergies to propylene glycol, lactic acid or vegetable glycerin;
- i) Adverse reactions when previously using electronic cigarettes;
- j) Unable to read for comprehension or completion of study documents (determined during the consenting/screening process);
- k) Unstable living environment that would compromise the ability to attend visits, sequester study products or complete study procedures outside of visits.

- l) Smoked marijuana use >9 times per month, and/or unwillingness to abstain from smoked marijuana during switch to study product (non-combusted forms of marijuana are acceptable)
- m) Medical history of thromboembolic events and/or cerebrovascular events, or medical diagnosis that the medical professional believes indicates a high risk of thromboembolic or cerebrovascular events.

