Tobacco constituent biomarkers

Nicotine is the major known addictive agent of tobacco and cigarette smoke,²² and a key component of most e-cigarette liquids. Nicotine exposure is measured by analyzing total nicotine equivalents (TNE), the sum of urinary total nicotine, nicotine-*N*-oxide, total cotinine, and total 3'-hydroxycotinine. TNE account for 73 – 96% of the nicotine dose²² and are an outstanding monitor of nicotine uptake.²² Tobacco-specific *N*-nitrosamines 4-(methylnitrosamino)-1-(3-pyridyl)-1-butanone (NNK) and NNN are likely causative agents for cancers of the lung, pancreas, oral cavity, and esophagus in tobacco users,²³⁻²⁵ and are classified as human carcinogens by the International Agency for Research on Cancer (IARC).^{24,25} NNN and NNK are present at relatively high levels in cigarette smoke, but only trace levels have been measured in e-cigarettes.^{13,26} Human exposure to NNK is measured by analyzing the sum of 4-(methylnitrosamino)-1-(3-pyridyl)-1-butanol (NNAL) and its glucuronides in urine; this validated and widely applied biomarker is referred to as total NNAL.²⁷⁻²⁹ Total NNAL correlates with cigarettes per day, nicotine equivalents in urine, and cotinine,^{30,31} and is an effective uptake marker for NNK.³² Human exposure to NNN is measured by analyzing the sum of unchanged NNN and its *N*-glucuronide excreted in urine (total NNN).^{33,34} Consistent with the known carcinogenicity of NNK and NNN, several nested case-control studies in smokers have demonstrated that urinary total NNAL is related to lung cancer and urinary total NNN is related to esophageal cancer risk.³⁵⁻³⁹ Thus, urinary NNAL and NNN are biomarkers of both exposure and cancer risk. Polycyclic aromatic hydrocarbons (PAH) are formed during the incomplete combustion of organic matter, always occur as mixtures, and many are potent carcinogens or toxicants in laboratory animals.^{40,41} PAH are widely accepted as major contributors to lung cancer in smokers,⁴¹⁻⁴⁴ and only trace levels of a few PAH have been reported in e-cigarettes.⁴⁵ 1-Hydroxypyrene (1-HOP) is an established biomarker of PAH exposure.³⁴ Certain volatile compounds such as acrolein, crotonaldehyde and propylene oxide are important toxicants and carcinogens in cigarette smoke,²⁹ and can also be formed upon heating and vaporization of propylene glycol and glycerin in e-cigarette aerosol. Acrolein is an intense irritant, causes cilia-toxicity in the lung, and is proposed to be a lung carcinogen,^{46,47} crotonaldehyde is a potent irritant and forms DNA adducts in the human lung,⁴⁸ and propylene oxide is an IARC Group 2B carcinogen. Acrolein, crotonaldehyde, and propylene oxide are excreted in the urine as 3-hydroxypropylmercapturic acid (3-HPMA), 3-hydroxy-1-methylpropylmercapturic acid (HMPMA), and 2-hydroxypropylmercapturic acid (2-HPMA), respectively. These biomarkers can be readily measured by established validated methods.⁴⁹⁻⁵² The structures of these urinary tobacco constituent biomarkers are illustrated in Figure 1.

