3.4 Safety Endpoints

- *Adverse Events Scale* assesses the nature, severity, duration, action taken, and outcome of adverse events related to tobacco product use;
- Potential adverse consequences: Change in mental (CESD) or physical health (heart rate, blood pressure, exhaled CO level, weight, Respiratory and Global Health Questionnaire, Health Changes Questionnaire, Adverse Events)
- Change in alcohol, substance use (Alcohol Use Questionnaire, Drug Use Questionnaire)
- Other tobacco product use

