Baseline period: (Baseline 1) Once the participant arrives to the clinic visit (University of Minnesota – Tobacco Research Programs, [name]), their vitals will be collected. Next, participants will be handed a carbon monoxide (CO) device and asked to blow into the machine. Participants of childbearing potential will be asked to provide a urine sample to test for pregnancy. Vitals collection, CO measurement and confirmation of pregnancy will be the final criteria to determine the subject's eligibility. If eligible, the participants will be shown how to complete the daily ITR and given a urine cup and instructions on how to collect their first morning void urine the morning of their next visit. They will be asked to return to the clinic one week later for Baseline 2. Upon arriving to Baseline 2, the first morning void urine will be collected and the daily ITR reviewed. Vitals and CO will be collected. Participants will be given a plastic cup and asked to rinse their mouth with tap water. This is done in preparation for the oral sample collection (saliva and buccal cells), which will occur at the end of visit, at least 20 minutes after the rinse. Participants will also be asked to complete several online surveys.

Participants will be provided counseling throughout the study to help them quit the use of cigarettes. Once assigned to SREC, the study coordinator will work with the participant to set a quit date approximately 3-5 days after assignment. In the period leading up to the quit date, participants will be encouraged to try the product and use it regularly to ensure the product and the study are a good fit for them. This approach is incorporated to maximize the likelihood that participants who proceed with the study will comply with the requirements. One day before the set quit date, the coordinator will schedule a zoom meeting with the participant to go over ways to quit and discuss the incentive program we are using to help them quit. Approximately one day after the set quit date, the coordinator will contact the participant to see how they are managing and discuss ways to address any barriers to quitting they are experiencing. Additional counseling will be available throughout the study as needed for each individual participant.

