Blood collection. Participants may opt in to have their blood drawn during this study. To attenuate the influence of diurnal variations and the influence of feeding status on the levels of inflammatory cytokines, the baseline visit and visits at weeks 4 and 6 will be held in the mornings. *If a subject cannot come in the morning for the clinic visit at baseline, weeks 4 or 6, the visit will be scheduled for a later time of the same day, and the subject will be offered to come for a blood draw in the morning of the day prior, or up to two days after, that visit.* Participants will be asked to fast (10 hours) prior to the scheduled visit. By opting in, participants are agreeing to have their blood drawn in the morning (before 11:00 am) under fasting conditions. Two 10 mL EDTA tubes will be drawn.

Intervention period: The study calendar is based off of the quit date and subjects will come to the clinic weekly for 4 weeks and at week 6. Biological samples will be collected at weeks 4 and 6 after the start of the assigned product use. Prior to the biological sample clinic visit, the participant will collect their first morning void urine. Once the participant arrives to the clinic, their first morning void urine will be collected. Next, they will be asked to rinse their mouth with tap water in preparation for the buccal cell collection. At each of the clinic visits, participants will provide a breath CO. If participant reports smoking or the CO is high (> 6 ppm), a brief compliance counseling session will be conducted to discuss any challenges the participant is facing. Tools to deal with these challenges will be provided. Their vitals will also be collected. Participants will be asked to complete the relevant online surveys (see **Table 3**). The ITR data will also be reviewed for completeness. Used and unused SREC pods will be collected, recorded, and new envelopes with the products will be dispensed to last until the next visit, as outlined below.

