| WEEK | 92 | 91 | 0 | 1 | 2 | 3 | 4 | 6 | 10 |
| Visit window | | 1 week | | | Can be done anytime during the week | | | 1 day, + 3 days | -1 day, + 3 days |
| Biological samples and biomarker measures | | | | | | | | | |
| Alveolar carbon monoxide (CO) | | X | X | X | X | X | X | X | |
| Vital signs | | X | X | X | X | X | X | X | |
| Urine Pregnancy tests* | | X | | X | | | X | X | |
| NicCheck Test (if applicable) | | X | X | | | | | | |
| First morning void urine (for urinary biomarkers according to Aims 1-3) | | | X | | | | X | X | |
| Blood collection (morning, fasting)***** | | | X | | | | X | X | |
| Oral cells | | | X | | | | X | X | |
| Saliva | | | X | | | | X | X | |
| Subjective measures | | | | | | | | | |

PROTOCOL TITLE: Biomarkers in SREC Users

VERSION DATE: 03/13/2024

| | | | | | | | | | |
|--|---|---|---|---|---|---|---|---|---|
| Demographics Questionnaire | x | | | | | | | | |
| Tobacco Use History and Exposure | x | | | | | | | | |
| Nicotine Dependence (FTND)** | | | x | | | | | | |
| E-Cigarette Dependence (PS-ECDI) | | | | | | | | x | |
| Environmental Tobacco Smoke Exposure | | | x | | | | x | | |
| Occupational & Environmental Toxicants | | | x | | | | x | | |
| Brief Medical History | x | | | | | | | | |
| Concomitant Medications | x | | x | x | x | x | x | x | |
| Prime MD | x | | | | | | | | |
| CESD | x | | | | | | x | x | |
| Alcohol Use Questionnaire*** | x | | | | x | | | x | |
| Recreational Drug Use Questionnaire*** | x | | | | x | | | x | |
| Respiratory and Global Health | | | x | x | x | x | x | x | |
| Health Changes Questionnaire | | | x | x | x | x | x | x | x |
| Adverse Events Scale | | | x | x | x | x | x | x | x |
| ITR product use recording | | x | x | x | x | x | x | x | |
| Timeline Follow Back (TLFB)***** | | | x | x | x | x | x | x | |
| Product Evaluation Scale | | | x | x | x | | x | x | |
| Purchasing Task***** | | | x | | | | | x | |
| Drug Effects/Liking**** | | | x | x | x | x | x | x | |
| Tobacco Use Status | | | | | | | | | x |

* Pregnancy tests may also be administered at clinic visits if last menstruation reported being more than 35 days ago.

** All subjects will be evaluated at baseline.

*** Use over the past 30 days at weeks 2 and 6.

**** Regular cigarettes will be evaluated at baseline for all subjects; at the following visits only SREC will be evaluated.

***** To be done if participant reports using other tobacco products on the daily ITR or if there is missing data in the ITRS

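### Smoked marijuana is permitted up to the baseline sample but not during the switch, so the fall in PheT can be modestly overstated; separately, the week-2 drug-use recall straddles the switch

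*Combined protocol and SAP*

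**What the plan says.** - **Eligibility (section 8.2, item l).** A candidate is excluded for "Smoked marijuana use >9 times per month", so up to 9 times a month is permitted at entry. The same item excludes "unwillingness to abstain from smoked marijuana during switch to study product (non-combusted forms of marijuana are acceptable". The required commitment is tied to the switch, and only smoke is at issue.
- **Baseline (section 5.2, Baseline period).** "Upon arriving to Baseline 2, the first morning void urine will be collected and the daily ITR reviewed". Saliva and oral cells are taken at the same visit, and SREC is first handed out there. Neither baseline visit carries an instruction about marijuana.
- **Follow-up (section 5.2, Intervention period).** "Biological samples will be collected at weeks 4 and 6 after the start of the assigned product use".
- **Calendar.** Section 5.2 states: "The study calendar is based off of the quit date". It places that date about 3-5 days after assignment. Table 3, however, labels Baseline 2 as week 0.
- **Drug-use measurement (Table 3).** The Recreational Drug Use Questionnaire is given at screening, week 2 and week 6, and not at Baseline 2. The footnote reads: "Use over the past 30 days at weeks 2 and 6". The alcohol form has the same schedule and footnote. Section 3.4 makes both a safety endpoint: "Change in alcohol, substance use (Alcohol Use Questionnaire, Drug Use Questionnaire".
- **Source of PAH (section 2.0).** "Polycyclic aromatic hydrocarbons (PAH) are formed during the incomplete combustion of organic matter". PheT is the PAH marker in Primary Aim 1 and Table 2.
- **Analysis (section 15.1).** The primary mixed model adjusts only for the baseline biomarker. The additional model gives environmental toxicants, stress and health as examples of covariates; marijuana is not named.

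**The concern.** The study is single-arm and compares each participant with his or her own baseline. Any exposure that stops when cigarettes stop is counted as an effect of switching to SREC. For a participant who smoked marijuana before Baseline 2 and then kept to item l, two sources of smoke are removed at once.

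Neither planned analysis separates them. Adjusting for the baseline biomarker does not help, because the baseline value itself carries the extra exposure. Restricting to verified complete switchers does not help either, because smoking status is checked for cigarettes and not for marijuana.

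At stake is the estimated percent change in PheT, which section 3.2 names as the measure for all biomarkers and which the study wants to publish as initial reference data. If marijuana smoke raises PheT, the error always favours SREC.

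The second issue is measurement. A 30-day recall at week 2 mixes days when smoked marijuana was permitted with days when it was not, so a reported use is hard to place. It also blurs the week-2 reading of the safety endpoint for drugs and alcohol.

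**Working it through.** **1. The plan's own power figure (section 15.2).** Inputs: log-scale SD 0.4, correlation 0.5, n = 15, alpha 0.001, 45% decrease, paired t-test.
- Effect: ln(0.55) = -0.598.
- SD of the difference: 0.4 × √(2 × (1 - 0.5)) = 0.40.
- Exact power from the noncentral t distribution on 14 df: 0.912 two-sided, 0.953 one-sided. The stated figure of more than 90% reproduces and is not disputed.
- Fall detectable with 90% power (two-sided): about 44% at n = 15 and 31% at n = 30.

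**2. Size of the spurious fall in PheT.** The documents give 9 uses a month (item l) and a minimum of 5 cigarettes a day (section 8.1, item b). They do not give the share of participants who smoke marijuana (q) or how many cigarettes one use is worth for PAH (k). Assumptions: q = 30%, all at the cap; k = 1 to 5; PheT proportional to total cigarette-equivalents over 30 days; these participants stop as item l intends.

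Marijuana's share of a user's baseline exposure is s = 9k / (9k + 30 × 5). The spurious fall in the geometric mean is 1 - (1 - s)^q, and a true 45% fall is observed as 1 - 0.55 × (1 - s)^q.

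| k | s | Spurious fall | True 45% seen as |
|---|---|---|---|
| 1 | 9/159 = 5.7% | 1.7% | 46.0% |
| 3 | 27/177 = 15.3% | 4.8% | 47.7% |
| 5 | 45/195 = 23.1% | 7.6% | 49.2% |

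At 10 cigarettes a day the shares fall to 2.9%, 8.3% and 13.0%, and the spurious falls to about 0.9%, 2.5% and 4.1%.

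**3. Could this alone reach significance?** With a paired t-test at alpha 0.001, the largest case in the table (k = 5) is declared significant with probability about 0.4% at n = 15 and 1.0% at n = 30. It could not by itself produce a significant result.

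**4. Recall windows.** Take the week-2 visit as day 14 and the week-6 visit as day 42.
- *Week 2, calendar from the quit date:* the window runs from day 14 - 30 = -16 to day 14. So 16 of 30 days (53%) precede the quit date. Baseline 2 lies 3-5 days before the quit date, so 16 - 5 = 11 to 16 - 3 = 13 days (37-43%) precede Baseline 2.
- *Week 2, calendar from Baseline 2 (Table 3):* 16 days precede Baseline 2.
- *Permitted use still reported at week 2* by a fully compliant participant at the cap: 9 × 11/30 = 3.3 to 9 × 13/30 = 3.9 uses on the quit-date calendar, or 9 × 16/30 = 4.8 on the Table 3 calendar.
- *Week 6:* the window runs from day 42 - 30 = 12 to day 42, after the switch on either calendar. It covers the 16 days before the week-4 sample (days 12-28) and all the time from then to week 6.

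**The case against.** The strongest reply is that the effect is small and confined to one marker. Use is capped, the sample is made up of daily cigarette smokers, and under the assumptions above the distortion is a few percentage points beside a planning effect of 45%. This stands, and it is why the priority is modest. It does not remove the point, because the error is systematic and affects a reported estimate, not only a test.

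It can also be said that the week-2 recall has no bearing on the biomarkers, since none is sampled then, and that comparing screening with week 6 gives a usable safety contrast. Both are largely right. What remains is that use in roughly the first 12 days after the switch cannot be placed, and that the week-2 reading of the safety endpoint mixes two periods. The questionnaire items are not reproduced, so the form may record dates or route of use.

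Finally, the additional model's covariate list is open-ended and could take a marijuana term. It could, but none is specified.

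Three stronger readings are tempting and are not supported:
- A reader might infer that the whole exposure panel is affected. The documents describe a source not specific to tobacco only for PAH. NNAL, NNN and TNE are tobacco or nicotine markers, and nothing shown establishes the point for the mercapturic acids or the effect markers.
- A reader might infer from Table 1, where 1-HOP stays at 96% of baseline in one switching study, that the PAH effect is small enough for marijuana to explain it. That study had only 9 complete switchers among 20. The other two show 43% and 30%, and this trial measures PheT.
- A reader might infer a bias near one fifth by assuming that 30% of participants have their baseline doubled: 1 - 2^(-0.3) = 19%. A participant at the cap has at most a 9/30 = 30% chance of use on a given day. On that daily reading every participant would have to be at the cap, and one use would have to equal a full day's cigarettes.

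**Conclusion.** The point holds for PheT. Baseline 2 and the week 4 and 6 samples are taken under different rules for a second source of smoke, and neither the design nor the stated models separates its removal from that of cigarettes. The fall in PheT can therefore be overstated in SREC's favour.

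The size rests on assumptions about prevalence and potency that the documents do not supply. With 30% of participants at the cap, 5 cigarettes a day and 1-5 cigarettes per use, it is about 2-8%, so that a true 45% fall is seen as about 46-49%. It is smaller for heavier smokers, or if fewer participants smoke marijuana or they do not stop.

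The recall problem is separate and limited to week 2 and the early switch period. A reader might infer that marijuana use after the switch goes unmeasured; the week-6 recall shows otherwise. Priority is modest: a small, directional bias that is cheap to reduce.

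**What to change.** 1. **Use one rule for all samples.** Apply the abstention from smoked marijuana from Baseline 1, so that Baseline 2 and weeks 4 and 6 are sampled under the same condition. The cost is one added instruction and about one extra week of abstention for people who have already agreed to about six. The documents do not say whether a week fully clears PheT, but the rule would at least be the same at each sample.
2. **For participants already sampled,** use the screening drug-use data for a PheT sensitivity analysis that excludes, or adjusts for, those who smoked marijuana at baseline. First check that the screening form identifies smoked use and over what period, since neither is stated. No new data collection is needed.
3. **Reword the week-2 drug and alcohol recall** to the period since Baseline 2 and report use per week, so that windows of different length can be compared. That period is about 14 days on the Table 3 calendar, or 14 + 3 = 17 to 14 + 5 = 19 days if weeks run from the quit date; state which calendar applies. The cost is a wording change on two existing forms.

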8.3 Screening

Cigarette smokers will be first pre-screened for eligibility over the telephone or online. If subjects meet the initial eligibility criteria for the study, they will be asked to complete a remote screening visit (completed via secured video-conferencing meeting link) where the entire study will be explained in detail, informed consent will be obtained and the screening questionnaires will be completed.

